7.4.3. Progression-Free Survival

Progression-free survival is defined as the number of days from the date of first dose (which is not necessarily Day 1) to the earlier of death or disease progression. Date of death will be determined using the Death Report, the Survival Follow-Up, and the Subject Status eCRFs. Disease progression is measured by investigator assessment of objective radiographic disease assessments per Lugano Classification. Censoring for PFS will follow the algorithm outlined in Table 3, which is based on FDA guidance (FDA 2007). The analyses will be based on the ITT population, according to treatment assignment. Time-to-event data will be analyzed by the Kaplan-Meier method, treating subjects with no observed death or progression as censored at the last valid radiologic assessment visit. Median PFS and 90% CI will be estimated.

Table 3: Evaluation and Censoring of Progression-Free Survival

Situation	Outcome	Date of Progression or Censoring
No baseline tumor assessments	Censored	Date of enrollment
Progression documented between scheduled visits	Progressed	Earliest of: 
 • Date of radiological assessment showing new lesion (if progression is based on new lesion); or • Date of last radiological assessment of measured lesions (if progression is based on increase in sum of measured lesions)
No progression	Censored	Date of last valid radiologic assessment (not NE and not missing)
Treatment discontinuation for undocumented progression	Censored	Date of last valid radiologic assessment (not NE and not missing)
Treatment discontinuation for toxicity or other reason	Censored	Date of last valid radiologic assessment (not NE and not missing)
New anticancer treatment started	Censored	Date of last valid radiologic assessment (not NE and not missing)
Death before first pharmacodynamic assessment	Progressed	Date of death
Death between adequate assessment visits	Progressed	Date of death
Death or progression after more than 1 missed assessment	Censored	Date of last valid radiologic assessment (not NE and not missing)

7.4.4. Overall Survival

Overall survival will be determined from the date of first dose until death. Survival data will be analyzed using Kaplan-Meier method, treating subjects with no observed death as censored at their last date known to be alive. Median survival and 90% CI will be estimated. Overall survival data will continue to be collected until 75% of subjects have died, have withdrawn consent, or are lost to follow-up.

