2.1.2.2. Secondary Objectives

The secondary objectives of Phase 2 are as follows:

- To evaluate efficacy in terms of duration of response (DOR), durable response rate, and PFS.
- To evaluate the safety and tolerability of the treatment combination.

[REDACTED]

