4.5. Overall Study Duration

The study begins when the first subject signs the ICF. The end of Phase 1 will occur when all subjects have completed the DLT surveillance period; Phase 2 will end once the last subject is assessed for response.

Once the last subject is evaluable for response, a database lock of the study will occur to allow the analysis of the study data. Any remaining subjects may continue to receive study treatment and be seen by the investigator per usual standard of care for this population. Provisions will be made to ensure access to treatment for subjects who are continuing to benefit from study treatment at the time of study termination.

The investigator will be expected to monitor for and report any SAEs, AEs of special interest, and pregnancies, as detailed in Section 8. The remaining subjects are considered to be on study until a discontinuation criterion is met and written notification is provided to the sponsor.

The study will end once all subjects have discontinued study treatment and safety follow-up.

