6.4. Follow-Up

6.4.1. Safety Follow-Up

The safety follow-up period is the interval between the EOT visit and the scheduled follow-up visit, which should occur 30 to 35 days after the EOT visit (or after the last dose of study drug if the EOT visit was not performed). Adverse events and SAEs must be reported up until at least 30 days after the last dose of study drug, the date of the follow-up visit, or until toxicities resolve, return to baseline, or are deemed irreversible, whichever is longer. Reasonable effort should be made to have the subject return for the follow-up visit and report any AEs that may occur during this phase.

If a subject is scheduled to begin a new anticancer therapy before the end of the safety follow-up period, the safety follow-up visit should be performed before new anticancer therapy is started.

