6.4.2. Disease Status Follow-Up

Subjects who discontinue study treatment for a reason other than disease progression will move into the disease status follow-up period and should be assessed per standard of care to monitor disease status. Every effort should be made to collect information regarding disease status until:

- The start of new antineoplastic therapy.
- Disease progression.
- Death.
- The end of the study.

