2.2.2.2. Secondary Objectives

The secondary objectives of Phase 2 are as follows:

- To evaluate efficacy in terms of DOR, durable response rate, PFS, and OS.
- To evaluate the safety and tolerability of the treatment combination.

[REDACTED]

- [REDACTED]
- [REDACTED]
- [REDACTED]

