2.3.2.2. Secondary Endpoints

- DOR, defined as the time from earliest date of disease response until earliest date of disease progression.
- Durable response rate, defined as the percentage of subjects achieving a CR or PR for > 16 weeks.
- PFS, defined as the time from enrollment until the earliest date of disease progression determined by objective radiographic disease assessments, or death due to any cause.
- OS, defined as the date of enrollment until death due to any cause.
- Safety and tolerability via assessment of the frequency, duration, and severity of AEs and SAEs, and changes in clinical and laboratory assessments.

[REDACTED]

- [REDACTED]
- [REDACTED]

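### SAP Amendment 2 still plans an overall survival analysis that Protocol Amendment 5 no longer contains and no longer collects data for

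*SAP*

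**What the plan says.** SAP Amendment 2 is dated 29 NOV 2022. Section 2.1 bases it on Protocol Amendment 5 of 18 JUN 2020, issued about 29 months earlier.

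The SAP keeps OS throughout:

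- Section 2.2.2.2 makes it a Phase 2 secondary objective: "To evaluate efficacy in terms of DOR, durable response rate, PFS, and OS".
- Section 2.3.2.2 makes it a secondary endpoint: "OS, defined as the date of enrollment until death due to any cause".
- Section 7.4.4 starts the clock elsewhere: "Overall survival will be determined from the date of first dose until death". It plans a median with a 90% confidence interval, censors subjects without a recorded death when last known alive, and adds: "Overall survival data will continue to be collected until 75% of subjects have died, have withdrawn consent, or are lost to follow-up".
- Appendix B lists Table 2.6.1, Figure 4.7.1 and Listing 2.6.3 for OS.
- Section 10.1, the place to declare departures from protocol-defined analyses, declares none. The change list in Section 10.2 does not mention OS.

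The corresponding objective in Protocol Section 2.1.2.2 reads: "To evaluate efficacy in terms of duration of response (DOR), durable response rate, and PFS". OS is also absent from the endpoints in Section 2.2.2.2 and from the analyses in Section 9.4.2.

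**The concern.** A SAP written for a named protocol version should analyse the endpoints that version defines, or say where it departs from them. This one presents OS as a protocol-based secondary result and commits to a collection rule that the protocol does not support.

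What is at stake is a published median OS. If follow-up stops near progression, censoring is not independent of the risk of death, and the Kaplan-Meier median need not estimate the population median. A reader of the study report would see a prespecified secondary endpoint, with no sign that the protocol had dropped it or that follow-up was uneven.

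**Working it through.** **What the current protocol collects after treatment ends**

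| Subject or event | Current protocol text | Later vital status collected? |
|---|---|---|
| Stops for progression | Section 6.4.1: safety visit, "which should occur 30 to 35 days after the EOT visit". Table 8 ends at this visit. | No |
| Stops for another reason | Section 6.4.2: "Subjects who discontinue study treatment for a reason other than disease progression will move into the disease status follow-up period". This follow-up ends at progression or new therapy. | Only until then |
| Late events | Sections 5.6.2, 6.4.1 and 8.3.2: unresolved toxicities, SAEs suspected to be related, second primary malignancies to 5 years | Only if such an event occurs |
| Whole study | Section 4.5: "The study will end once all subjects have discontinued study treatment and safety follow-up" | No extension for survival |

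The amendment summary in Appendix C agrees: removing OS was the stated purpose of Amendment 5.

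**The 75% rule as a count.** 0.75 × 60 = 45 subjects, or 0.75 × 22 = 16.5, so 17, if Phase 2 stops after Stage 1. Nothing in the protocol keeps the study open until either count is reached.

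**Two start dates.** Protocol Section 6.1 requires treatment within 2 days of enrollment, so the two origins differ by at most about 2 days for treated subjects. The wording needs aligning, but the numerical effect is negligible.

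**Possible bias (illustration; every input is assumed).** Times are exponential. Median time to progression is 3 months, from progression to death 3 months, and to death without progression 20 months. Last contact is 32 days (1.051 months) after progression.

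- Monthly rates: λ₁ = ln2/3 = 0.2310 (progression), λ₂ = ln2/20 = 0.0347 (death without progression), μ = ln2/3 = 0.2310 (death after progression). Let a = λ₁ + λ₂ = 0.2657.
- True survival: S(t) = e^(−at) + (λ₁/λ₂)(e^(−μt) − e^(−at)). At t = 6.2: 0.1926 + 6.667 × (0.2387 − 0.1926) = 0.500. The true median is 6.2 months.
- No subject followed past day 32 after progression: once the first 32 days from entry have passed, the ratio of progressed to unprogressed subjects at risk is r = 6.667 × (e^(0.0347 × 1.051) − 1) = 0.247. The hazard that Kaplan-Meier sees is (0.0347 + 0.2310 × 0.247)/1.247 = 0.0736. ln2/0.0736 = 9.4 months. The lower hazard in the first 32 days moves the median to 9.7.

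Kaplan-Meier medians in months, by share of subjects fully followed (simulation, 400,000 subjects per case):

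| Medians: progression / post-progression / death without progression | Last contact | True | 0% | 25% | 50% | 80% |
|---|---|---|---|---|---|---|
| 3 / 3 / 20 | 32 days | 6.2 | 9.7 | 7.7 | 6.9 | 6.4 |
| 4 / 4 / 20 | 32 days | 7.9 | 12.5 | 9.8 | 8.8 | 8.2 |
| 3 / 3 / 10 | 32 days | 5.4 | 7.0 | – | 5.8 | 5.5 |
| 3 / 3 / 40 | 32 days | 6.7 | 12.0 | – | 7.7 | 7.0 |
| 3 / 3 / 20 | 60 days | 6.2 | 7.7 | – | 6.6 | – |

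**Reversal.** Suppose every later death is recorded but later alive-dates are not, with time from entry to cutoff uniform over 12, 18 or 24 months. In the 3/3/20 case the median becomes 5.6, 5.8 or 5.9 months against a true 6.2. If half of the later deaths are recorded it becomes 6.5, 6.6 or 6.7.

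**The case against.** The strongest reply is that OS data probably exist. SAP Section 7.4.3 names a Survival Follow-Up eCRF, Section 2.1 cites CRFs approved on 02 NOV 2016, and survival follow-up was in the protocol until June 2020. Participation was expected to average about 6 months, so much of the follow-up, perhaps even the 75% count, could have been complete by then. If so, the 0% column is unrealistic. At 80% followed the bias is about 0.2 month, small against sampling error: under the 3/3/20 assumptions with 60 subjects, the 5th to 95th percentiles of the estimated median are 4.9 to 7.5 months with complete follow-up and 5.1 to 8.1 with 80%. Event-driven contact and the Death Report and Subject Status eCRFs may add later dates, and the direction of bias is not certain. OS also carries no test or decision rule.

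All of this stands as a limit on the size of the problem, and it means that the documents do not prove data to be missing. It does not remove the mismatch. The SAP does not restrict OS to data gathered before the amendment, sets no cutoff, does not say how many subjects were followed, and states that collection will go on.

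**Conclusion.** The concern holds. That the SAP plans an endpoint absent from its governing protocol, without declaring it, follows directly from the current text of both documents. So does the lack of a procedure to support the 75% rule for subjects followed under Amendment 5.

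Bias in the median is a risk of unknown size. It is expected to be upward to the extent that subjects were followed only under Amendment 5 and their later deaths went unrecorded. It would be downward if deaths were captured but alive-dates were not. The illustrative range runs from about 0.2 month at 80% followed to 3.5 months at 0% (9.7 − 6.2), and it rests wholly on assumed inputs.

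The response-rate analysis, alpha, power and the threshold of 29 responders are unaffected. The point should be fixed, but it does not threaten the trial's primary conclusion.

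**What to change.** Choose one of two routes.

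1. Delete OS from SAP Sections 2.2.2.2, 2.3.2.2 and 7.4.4, and remove Table 2.6.1, Figure 4.7.1 and Listing 2.6.3.
2. Keep OS, but declare it in SAP Section 10.1 as an exploratory descriptive analysis outside the protocol. Use one start date and drop the 75% rule. Set a single calendar cutoff for all subjects, no later than the date on which survival follow-up actually stopped, and report how many subjects were followed to it. This route suits the case where useful survival data were collected before the amendment.

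Under either route, reconcile the Survival Follow-Up eCRF named in SAP Section 7.4.3 with the current protocol. Do not remove any validly recorded death from progression-free survival because of this change.

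The cost is SAP wording and the removal or relabelling of one table, one figure and one listing. The second route also needs a review of existing data to count the subjects followed. Neither route needs new data.

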7.4.5. Other Efficacy Analyses

7.4.5.1. Eastern Cooperative Oncology Group Performance Status

Subjects' ECOG performance status and changes in status at scheduled assessment times will be summarized.

7.4.5.2. Weight

Subjects' body weight and change from baseline in body weight at scheduled assessment times will be summarized.

[REDACTED]

[REDACTED]

8. SAFETY AND TOLERABILITY

A list of planned tables, figures, and listings is provided in [Appendix B](#).

8.1. General Considerations

The analyses for this section will be provided mainly for the Phase 2 portion using the safety evaluable population. Data from the Phase 1 portion using the safety run-in population will be summarized separately where appropriate. Summary tables may be replaced with listings when appropriate. For instance, an AE frequency table may be replaced with a listing if it only contains a few unique preferred terms reported on relatively few subjects. Additional summaries for specific subgroups may be included on an ad hoc basis.

8.2. Adverse Events

8.2.1. Adverse Event Definitions

A TEAE is any AE either reported for the first time or worsening of a pre-existing event after first dose of study drug and until 30 days after the last dose of study drug. Analysis of AEs (as discussed below) will be limited to TEAEs, but data listings will include all AEs regardless of their timing to study drug administration.

Adverse events will be tabulated by the MedDRA preferred term and system organ class. Severity of AEs will be described and graded using the NCI CTCAE v4.03. The CTCAE reporting guidelines and grading details are available on the Cancer Therapy Evaluation Program website ([NCI 2010](#)).

A grading (severity) scale is provided for each AE term. If the toxicity is not included in the CTCAE v4.03 criteria, then it will be rated on a scale of 1 to 4 as follows: 1 = mild, 2 = moderate, 3 = severe, and 4 = life-threatening. All toxicities will be graded based on the worst level reached, not the level that they may have reached if they had not been treated. When the intensity of an AE changes over time for a reporting period (eg, between visits), each change in intensity will be collected as an AE until the event resolves. Only the worst grade will be reported in AE summaries. Also, the Grade 3 or higher AEs will be reported in the listing to display all higher intensity AEs.

The subset of AEs considered by the investigator to be related to INCB039110 or ibrutinib will be considered to be treatment-related AEs. If the investigator does not specify the relationship of the AE to study drug, then the AE will be considered to be treatment-related. The incidence of AEs and treatment-related AEs will be tabulated. Serious adverse events will also be tabulated.

Any missing onset date, causality, or severity must be queried for resolution. Unsolved missing values will be handled according to the following rules:

- An unsolved missing causality will be considered treatment-related.
- An unsolved missing severity will be identified as an unknown severity.

For purposes of analysis, all AEs will be considered TEAEs unless the AE can unequivocally be defined as not treatment-emergent. Therefore, an unsolved missing onset date will be considered treatment-emergent, with the following exceptions:

- If the stop/resolution date is before the first dose administration date on Day 1, then the AE will be considered as not being treatment-emergent.
- If both the month and day are missing, and the last day of the year is before the first dose administration date on Day 1, then the AE will not be considered treatment-emergent.
- If only the day is missing, and the last day of the month is before the first dose administration date on Day 1, then the AE will not be considered treatment-emergent.
- If only the day is missing, and the first day of the month is after the first dose administration date on Day 1, then the AE will be considered treatment-emergent.

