8.3.2. Reporting

Every SAE, regardless of suspected causality (eg, relationship to study drug(s) or study procedure or disease progression), occurring after the subject has signed the ICF through the last study visit (or 30 days after the last dose of study drug, whichever is later) must be reported to the sponsor (or designee) within **24 hours** of learning of its occurrence, unless otherwise specified by the Protocol. Any SAEs occurring more than 30 days after the last dose of study drug should be reported to the sponsor or its designee only if the investigator suspects a causal relationship to the study drug.

Information about all SAEs is collected and recorded on the Adverse Event form of the eCRF. The investigator must assess and record the causal relationship of each SAE to the study treatment.

The investigator must also complete the Incyte Serious Adverse Event Report Form, in English, and send the completed and signed form to the sponsor or designee within 24 hours of becoming aware of the SAE. The investigator must provide a causality assessment, that is, assess whether there is at least a reasonable possibility that the SAE is related to the study treatment: suspected (yes) or not suspected (no). Refer to the Incyte Reference Guide for Completing the Serious Adverse Event Report Form.

The contact information of the sponsor's study-specific representatives is listed in the investigator manual provided to each site. The original copy of the SAE Report Form and the confirmation sheet must be kept at the study site.

Investigational site personnel must report any new information regarding the SAE within 24 hours of becoming aware of the information in the same manner that the initial SAE Report Form was sent. Follow-up information is recorded on an amended or new SAE Report Form, with an indication that it is follow-up to the previously reported SAE and the date of the original report. The follow-up report should include information that was not provided on the previous SAE Report Form, such as the outcome of the event (eg, resolved or ongoing), treatment provided, action taken with study drug because of the SAE (eg, dose reduced, interrupted, or discontinued), or subject disposition (eg, continued or withdrew from study participation). Each recurrence, complication, or progression of the original event should be reported as follow-up to that event, regardless of when it occurs.

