If the SAE is not documented in the IB for the study drug (new occurrence) and is thought to be related to the sponsor's study drug, the sponsor or its designee may urgently require further information from the investigator for reporting to health authorities. The sponsor or its designee may need to issue an Investigator Notification (IN) to inform all investigators involved in any study with the same drug that this SAE has been reported. Suspected Unexpected Serious Adverse Reactions (SUSARs) will be collected and reported to the competent authorities and relevant ethics committees in accordance with Directive 2001/20/EC, or as per national regulatory requirements in participating countries.

All new malignant tumors including solid tumors, skin malignancies, and hematologic malignancies will be reported as SAEs, regardless of the treatment group that the subject is enrolled in.

This includes any second primary malignancy, regardless of causal relationship to study drug(s), occurring at any time for the duration of the study, from the time of signing the informed consent to 5 years after the last study drug treatment.

Events of second primary malignancy are to be reported using the SAE form; these events must also be documented in the appropriate page(s) of the eCRF and in the subject's source documents. Documentation of the diagnosis of the second primary malignancy must be provided at the time of reporting as an SAE (eg, any confirmatory histology or cytology results, x-rays, CT scans).

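### The missing-onset-date rules for adverse events ignore the 30-day end of the TEAE window, so a clearly late event counts as treatment-emergent if its day is missing

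*SAP*

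**What the plan says.** SAP 8.2.1 gives the TEAE definition two ends: a TEAE is an AE that is new or worsens "after first dose of study drug and until 30 days after the last dose of study drug". AE analyses are restricted to TEAEs, while the listings show every AE.

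Missing onset dates must first be queried. For those that stay unresolved, the SAP states a principle, that "all AEs will be considered TEAEs unless the AE can unequivocally be defined as not treatment-emergent", and derives a default from it: "an unsolved missing onset date will be considered treatment-emergent, with the following exceptions". The list that follows has four items:

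- **Stop date known.** "If the stop/resolution date is before the first dose administration date on Day 1, then the AE will be considered as not being treatment-emergent".
- **Year only.** "If both the month and day are missing, and the last day of the year is before the first dose administration date on Day 1", the AE is not a TEAE.
- **Day missing, month entirely before first dose.** Not a TEAE.
- **Day missing, month starting after first dose.** If "the first day of the month is after the first dose administration date on Day 1, then the AE will be considered treatment-emergent".

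The protocol provides for events beyond the window. Section 8.3.2 covers late SAEs that the investigator suspects are related ("Any SAEs occurring more than 30 days after the last dose of study drug should be reported") and second primary malignancies, reported as SAEs "from the time of signing the informed consent to 5 years after the last study drug treatment".

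**The concern.** The definition has a start and an end, but the date rules test only the start. None of the four items mentions the last dose or the 30 days after it. The last item is also mandatory: once the month begins after first dose the AE is a TEAE, however long after treatment that month falls.

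Treating doubtful dates as treatment-emergent is a sound convention and is not in question. The fault lies with dates that leave no doubt. If the earliest day consistent with a partial date is already past the window, every possible completion is outside the definition, and the SAP's own principle would exclude the event.

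Two identical late events can therefore be classified differently only because one site recorded the day and the other did not. Most ordinary AEs are collected only to about 30 to 35 days after treatment, so late records will mainly be suspected-related SAEs and second malignancies. Any error then falls mainly in the serious, treatment-related serious and fatal TEAE tables, where counts are small.

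**Working it through.** The plan gives no figure to reproduce. The check applies the rules as written to partial dates and compares the result with the classification a complete date would receive.

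**Inputs from the documents**
- Window for a complete date: first dose to last dose + 30 days (SAP 8.2.1).
- Partial-date rules: the four items and the default (SAP 8.2.1).
- Planned Phase 2 numbers: 22 in Stage 1, 60 in total (Protocol 4.3.1).

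The treatment dates below are assumed for illustration.

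**Example 1: last dose 10 August 2018**
- Window end = 10 August + 30 days = 9 September 2018.
- Onset December 2018, day unknown: the earliest possible date is 1 December. Days after last dose = 21 (rest of August) + 30 + 31 + 30 + 1 = 113. Since 113 > 30, no day in that month is inside the window. The last rule nevertheless makes it a TEAE.
- Onset 2019, month and day unknown: the earliest possible date is 1 January 2019, which is 113 + 31 = 144 days after last dose. The year does not precede first dose, so the default makes it a TEAE.
- Onset 1 December 2018 recorded in full: outside the window, not a TEAE.

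**Example 2: first dose 10 January 2018, last dose 15 May 2018, window end 14 June 2018**

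| Recorded onset | Earliest possible onset, days after last dose | Any complete date a TEAE? | Rules as written | With an end-of-window test |
|---|---|---|---|---|
| Dec 2017 | before first dose | no | not TEAE | not TEAE |
| Jan 2018 | during or before treatment | some | TEAE | TEAE |
| Mar 2018 | during treatment | all | TEAE | TEAE |
| Jun 2018 | 17 | some | TEAE | TEAE |
| 2018 (year only) | before or during treatment | some | TEAE | TEAE |
| Jul 2018 | 47 | none | TEAE | not TEAE |
| Sep 2018 | 109 | none | TEAE | not TEAE |
| 2019 (year only) | 231 | none | TEAE | not TEAE |
| Mar 2020 | 656 | none | TEAE | not TEAE |
| May 2023 | 1812 | none | TEAE | not TEAE |

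The rules as written misclassify the last five rows. An end-of-window test corrects those five and changes nothing else; the ambiguous dates stay treatment-emergent.

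**Effect on a rate.** One added subject shifts a proportion by 1/n: 1/22 = 4.5 percentage points, 1/60 = 1.7 points. This applies to the overall serious-TEAE rate only if the subject has no other serious TEAE. Otherwise only the system organ class or preferred term rows can change.

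**The case against.** The strongest reply is that the SAP's governing sentence already settles the matter. An onset in December against a window that closed in September is unequivocally not treatment-emergent, so a careful programmer would exclude it. The year-only case is weaker still as a contradiction, since no rule states the wrong answer and only the default produces it. This shows what the SAP intends, but it does not repair the text. The principle is put into effect through a list of exceptions, none of which concerns the end of the window, and for a missing day the last item expressly directs the opposite result.

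The second reply is rarity, and it largely stands. The date must remain incomplete after a query. The event must start more than 30 days after last dose, when collection is narrow. Late SAEs and second malignancies are also among the best documented events: SAEs are due within 24 hours of awareness, and second malignancies need supporting documentation of the diagnosis. How many would come years after treatment is uncertain, because Protocol 8.3.2 also ties second-malignancy reporting to the duration of the study, and Protocol 4.5 ends the study once treatment and safety follow-up are complete. The defect does not depend on that, since a gap of weeks or months is enough.

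It is also true that the error can only over-count, that there is no comparison between arms, and that the listings show every AE. These points limit the harm; they do not make the rule correct.

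**Conclusion.** The concern holds: the missing-date rules in SAP 8.2.1 are wrong as written. They assign TEAE status to events that cannot meet the TEAE definition in the same section, and that status depends on how completely the date was recorded.

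The consequence is small. It is confined to partial onset dates unresolved after query and lying wholly beyond last dose + 30 days, and the documents do not say how many to expect. The shifts of 4.5 and 1.7 points describe a single hypothetical subject with no other serious TEAE, at the planned Phase 2 sizes. The primary endpoint, the Simon rule and the Day 28 DLT assessment are unaffected. The point deserves a correction but does not threaten the study's conclusions.

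**What to change.** Make two edits to SAP 8.2.1:

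1. Add an exception: *If the earliest possible onset date (the first of the known month, or 1 January of the known year) is later than 30 days after the last dose of study drug, the AE is not treatment-emergent.*
2. Bound the last rule: *If only the day is missing and the month starts after first dose and no later than 30 days after the last dose, the AE is treatment-emergent.*

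The SAP should also state which date counts as the last dose when the two drugs stop on different days, and that the end test does not apply to a subject still on treatment at database lock.

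The cost is two sentences, that clarification and one condition in the derivation. Ambiguous dates remain treatment-emergent and every AE still appears in the listings, so no safety information is lost.
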